4.3.3 Regional SUVR

Mean SUVR change from baseline will be evaluated for each of the selected brain regions of interest such as frontal, temporal, parietal, occipital and precuneus. The corresponding reference region will be the whole cerebellum. The SUVR is computed as the ratio of the target region signal to the reference region signal.

4.4 Safety Variables

The safety analysis will be based on the reported adverse events and other safety information including:

- Local tolerability at injection site
- Vital signs
- Physical examination
- 12-lead ECG
- Laboratory tests: hematology, clinical chemistry (HbA1c, glucose AC, AST, ALT, bilirubin, sodium, total protein, BUN, creatinine, potassium, and albumin), and inflammatory parameters (CRP, ESR, TNF- α , IL-6, and IL-8)

- Imaging variables:
 - Amyloid-related imaging abnormality-E (ARIA-E) which includes parenchymal vasogenic edema and/or sulcal (leptomeninges) effusion
 - Amyloid-related imaging abnormality-H (ARIA-H) which includes hemosiderin deposits such as microhemorrhage and superficial siderosis
 - Post-vaccine meningoencephalitis (PVM)
 - Age-related white matter changes (ARWMC)
 - Non-ARIA abnormalities

5 STATISTICAL METHODS

5.1 General

Continuous data will be summarized by treatment group using the number of observations available (n), mean, standard deviation (SD), median, interquartile range (IQR), minimum, and maximum.

Categorical data will be summarized by treatment group using count and percentage. Missing data will not be categorized in the summaries.

In general, descriptive statistics of quantitative efficacy and safety parameters (results and changes from baseline) by scheduled visit will be provided on observed cases, i.e. the inclusion of only subjects with non-missing assessments at a specific visit.

For undetected value, this study will take the minimum value that can be detected as the text value, eg, <3.5 will be treated as 3.5 and <0.012 will be treated as 0.012 when performing the summary and will list the original value in listing.

- The pre-treatment period is defined as the time from the date of the informed consent to the time before the administration of first dose of study medication.
- The post-treatment period is defined as the time from after the first dose of study medication to the end of the study.

All statistical tests will be two-sided at the alpha level of 0.05, unless otherwise specified.

5.2 Handling of Dropouts or Missing Data

Partial date of initial diagnosis will be imputed as below:

- If year is missing (or completely missing), do not impute;
- 15th of the month will be used to impute the initial diagnosis date if only the day is missing;
- 01July of the year will be used to impute as the initial diagnosis date if both the day and the month are missing;

ADAS-Cog total score

- The imputed total score of ADAS-Cog-13 when there is only one item is missing due to non- cognitive reasons is presented in:

Missing Question	Imputed Total formula
Word Recall	Observed Total*(1+10/75)
Orientation	Observed total*(1+8/77)
Word Recognition	Observed total*(1+12/73)
Delayed Word Recall	Observed Total*(1+10/75)
All other questions	Observed total*(1+5/80)

- If more than one of 13 items of ADAS-Cog are missing/NA, the total score will be set to missing.

Concomitant Medications Start/End Date

Partial missing start/end date to concomitant medications will be imputed as below:

Start date of concomitant medications

- If only the day of the month is missing, use the first day of the month to replace the missing part.
- If both the day and the month are missing, January 1st will be used to replace the missing part.
- If Day, Month and Year are all missing, use a date one day before the first date of study drug.

End date of concomitant medications

- If only Day is missing, use the last day of the month.
- If Day and Month are both missing, use the last day of the year.
- If Day, Month and Year are all missing, assign ‘continuing’ status to stop date.

Adverse Event Start/End Date

Missing or partial missing date to the onset date of AE will be imputed as below:

- If the AE onset date is completely missing, the AE start date will be imputed as the first date of study drug;
- If the AE onset date is partial missing, then If both the year and the month are available and the year and the month are the corresponding year and month of the first dosing date, then the AE start date will be imputed as the first dosing date;
 - If both the year and the month are available and the year and the month are not equal to the corresponding year and month of the first dosing date, then the AE start date will be imputed as the 1st date of the month;
 - If only the year is available and the available year is the corresponding year of the first dosing date, then the AE start date will be imputed as the first dosing date;
 - If only the year is available, and the available year is not equal to the corresponding year of the first date of study drug, then the AE start date will be imputed as the January 1st of the year;

Adverse event end date will be imputed as below for the partial date only.

- If both the year and the month are available, AE end date will be imputed as the last day

- of the month;
- If only the year is available, AE end date will be imputed as the December 31st of the year.
- If the AE onset date is completely missing and status is “ongoing”, it will not be imputed

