### 4.2 Inclusion Criteria

For inclusion in the study subjects must fulfil all of the following criteria:

1. Male or female aged between 60-90 years old.
2. Probable Alzheimer's disease based on the National Institute of Neurological and Communicative Disorders and Stroke and the Alzheimer's Disease and Related Disorders Association (NINCDS-ADRDA) criteria and National Institute on Aging-Alzheimer's Association (NIA-AA) guidelines.
3. Mini-Mental State Examination (MMSE) scores between 20 and 26 (inclusive).
4. Clinical dementia rating (CDR) scores of 0.5 or 1.
5. At least 6 years of education or sufficient work history (to exclude mental retardation).
6. Visual and auditory acuity adequate for neuropsychological testing.
7. Stable doses of permitted medications for 3 months before screening, such as acetyl cholinesterase (AChE) inhibitors, N-methyl-D-aspartate (NMDA) receptor antagonist, ergot alkaloids or their derivatives for cognitive enhancement.
8. Hachinski ischemic score (HIS)  $\leq 4$  (original score).
9. Geriatric Depression Scale-Short Form (GDS-SF)  $< 6$ .
10. Eastern Cooperative Oncology Group (ECOG) performance status 0-2.
11. Female must either be post-menopausal (no menstrual period for  $> 1$  year), surgically sterilized or agree to avoid becoming pregnant during the entire period of this study; while sexually active fertile male must agree to use effective birth control methods throughout the study duration, if their sexual partner(s) are women of childbearing potential.
12. With a caregiver who has frequent contact with the subject (e.g. an average of 10 hours per week or more) and agrees to sign the informed consent form (ICF), to perform study-related AD scales and to accompany or delegate a companion with the subject to all visits. A companion needs not to be a family member (with kinship).
13. Both patient and his/her caregiver should sign the written informed consent before undergoing any study procedures.
14. Agree not to donate blood or blood products for transfusion during the study and for 3 months thereafter.

15. A positive of A $\beta$  plaque on 18F-AV-45 PET by an imaging expert (confirmed during the second stage of screening per central independent review).

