4 ANALYSIS VARIABLES

4.1 Demographic and Baseline Characteristics

The baseline value is defined as the last available value before the first injection of study drug. The following demographic and baseline disease characteristics will be summarized by treatment, by study center and overall for the randomized and treated population.

Demographic characteristics are defined as follows:

- Age (in years) to be derived as: (date of informed consent - date of birth)/365.25
- Gender (male/female)
- Body weight (kg)
- Body Mass Index (BMI, kg/m²): weight in kg/(height in meters)²
- Race

Disease characteristics including:

- Disease duration (years): (date of informed consent– date of diagnosis)/365.25
- APOE genotype
- Baseline scores of ADAS-Cog total score, MMSE total score, ADCS-ADL total score, CDR/CDR-SB total score, NPI total score

Inflammatory markers including:

- CRP
- ESR
- TNF- α
- IL-6
- IL-8

Physical examination, medical history and concomitant disease, previous and concomitant medication, and HIS score will be described at baseline.

The baseline safety data of clinical chemistry and hematology, inflammatory markers and number of microhemorrhages in the brain will also be summarized.

4.2 **Immunogenicity Variables**

The level of anti-A β antibodies is one of the primary endpoints and is assessed at baseline (V1) and every following visit (V2 to V13). The one-sided 95% confidence interval (CI, right side) from all visits (V1 to V13) for subjects in Arm 3 (placebo group) will be calculated as the threshold of response. Antibody responders will be defined as the subjects with serum antibody titer > response threshold at any visit after baseline.

Response rate, treatment difference and its 90% CI will be calculated.

The AUC of anti-A β antibodies will be served as exploratory endpoint. AUC will be calculated by the sum of individual trapezoid area under the curve of level of A β antibodies. In case of missing titer values, last observation carry forward will be used for AUC calculation.

4.3 **Efficacy Variables**

Efficacy variables are evaluated as secondary endpoints in this study.

The change from baseline in cognitive, functional, and global assessments through the end of the study

- Cognition: ADAS-Cog
 - The ADAS-cog 13 contains 13 items, with a total scoring range of 0 – 85 and higher scores indicating greater dysfunction.
- Cognition: MMSE

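### SAP 5.2 imputes partial diagnosis dates with no upper limit at informed consent, so disease duration can come out negative, by up to half a year

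*SAP*

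**What the plan says.** SAP 5.2 has two rules for an incomplete date of initial diagnosis. When only the day is unknown, "15th of the month will be used to impute the initial diagnosis date if only the day is missing". When day and month are unknown, "01July of the year will be used to impute as the initial diagnosis date if both the day and the month are missing". If the year is missing, nothing is imputed. SAP 4.1 then derives "Disease duration (years): (date of informed consent– date of diagnosis)/365.25". Neither document caps the imputed date at consent or checks the order of the two dates.

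Two neighbouring rules in SAP 5.2 matter for the accompanying corrections:

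- **Medication start.** Under a heading for concomitant medications: "If Day, Month and Year are all missing, use a date one day before the first date of study drug". It contains no check against a known stop date, and the SAP has no separate date rule for previous medications.
- **Adverse events.** The onset rules say "If the AE onset date is completely missing, the AE start date will be imputed as the first date of study drug". The last bullet of the list of end-date rules begins "If the AE onset date is completely missing and status is" ongoing, and concludes that no imputation is made.

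**The concern.** A midpoint rule is sensible when the whole year or month was available for the diagnosis. It fails when consent cuts that interval short. The rule can then place the diagnosis after the subject consented to a trial that requires the diagnosis, and the derived duration is negative.

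Disease duration is one of the disease characteristics used to describe the comparability of three arms of about 15. SAP 4.1 asks for it by treatment, by center and overall. SAP 5.1 requires the minimum to be shown, and SAP 5.7.1 tests baseline characteristics across arms. One negative value could therefore be printed as the minimum in several rows of the study report.

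**Working it through.** The plan gives no figure to reproduce, so the check applies its rules to calendar dates.

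**Inputs.** Imputed day: 1 July or the 15th (SAP 5.2). Duration = (consent − diagnosis)/365.25 (SAP 4.1). Planned arm size: 15 (SAP 5.13).

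1. **Year-only diagnosis, same year as consent.** Any consent from 1 January to 30 June precedes 1 July.
   - Example: consent 10 March 2017, diagnosis recorded as 2017. Duration = −113/365.25 = −0.31 years.
   - Worst case, consent on 1 January: −181/365.25 = −0.496 years (−182/365.25 = −0.498 in a leap year).

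2. **Day-missing diagnosis, same month as consent.** Consent on days 1 to 14 precedes the 15th.
   - Example: consent 5 March 2017, diagnosis March 2017. Duration = −10/365.25 = −0.03 years.
   - Worst case: −14/365.25 = −0.038 years.

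3. **Share of same-year, year-only diagnoses that turn negative.** This needs assumptions the documents do not supply, so here is a range (365-day year):
   - Consent uniform over the year: 181/365 = 49.6%.
   - All pairs of dates with diagnosis on or before consent in that year equally likely: (181 × 182)/(365 × 366) = 32,942/133,590 = 24.7%. Early consents count less because they leave less time for a same-year diagnosis.
   - The same, with diagnosis at least 90 days before consent: (91 × 92/2)/(275 × 276/2) = 4,186/37,950 = 11.0%.

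4. **Effect on an arm mean.** Moving the worst case up to zero shifts a mean of 15 by 0.496/15 = 0.033 years.

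5. **Effect of the midpoint fix on the example in step 1.** The earliest possible date is 1 January 2017, 68 days before consent. The midpoint is 4 February 2017 and the duration is 34/365.25 = 0.09 years. The arm mean moves by (34 + 113)/365.25/15 = 0.027 years.

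6. **Medication start.** A concomitant medicine, as SAP 5.7.4 defines it, is taken on or after first injection, so a start on Day −1 cannot follow its stop. If the rule is also used for previous medicines, a drug stopped 10 or 42 days before first dose gets a start 9 or 41 days after its stop.

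7. **Adverse event bullet.** Read literally, a completely missing onset is both set to first dose and, if the event is ongoing, left blank. Read as an end-date rule, which is what its list announces, there is no conflict.

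**The case against.** The strongest reply is that this hardly matters. Disease duration enters none of the models in SAP 5.9 or 5.10. The conditions for a negative value are narrow, a negative minimum would be noticed, and no partial diagnosis date is known to exist. All of that stands and limits the point to a minor one. It does not remove the defect: a stated rule can return a value that cannot be true, and finding it after unblinding would force an unplanned repair.

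A reader might go further in three ways that the documents do not support.

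- *The baseline tables will be wrong.* They can be, but the number of partial dates is not given. Quoting only the 50% figure would also overstate the share.
- *The medication rule undermines eligibility*, because a long-standing drug dated to Day −1 clashes with inclusion criterion 7, "Stable doses of permitted medications for 3 months before screening". Eligibility is checked at S1 and again at V1 (Protocol 8.1.1 and 8.1.3), before any imputation, so an imputed date cannot undo it. Start-after-stop needs a rule headed concomitant to be stretched to previous medicines. That is plausible, since no other rule exists, but SAP 5.7.4 reports counts by drug class, which would barely change; mainly the listed dates would be wrong.
- *Ongoing adverse events of unknown onset drop out of the treatment-emergent tables.* This requires a bullet in the end-date list to override the explicit onset rule. The natural reading is a slip of *onset* for *end*, and then no event is lost. Even on the literal reading, one record changes at most one subject (1/15 = 6.7 percentage points in an arm), and only if that subject has no other treatment-emergent event.

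**Conclusion.** The point holds as a minor one. The diagnosis-date rules lack a limit at consent and can return negative disease durations: to −0.50 years for year-only dates and −0.04 years for day-missing dates. The share of same-year, year-only diagnoses affected is about 11% to 50% under the three timing assumptions shown; the number of such records is unknown. Each affected subject moves an arm mean of 15 by at most about 0.03 years. The consequence is an impossible minimum in a descriptive table and a small disturbance to the baseline comparison. No immunogenicity or efficacy analysis is touched.

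This takes the diagnosis to be no later than consent, as the duration formula presupposes. A diagnosis first made during screening should have a full date, so imputation would not arise.

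The medication and adverse event wording needs tidying, but neither supports a claim that results are wrong.

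**What to change.** In SAP 5.2, add to the diagnosis-date rules: if the imputed date is later than informed consent, use the midpoint between the earliest possible date (1 January of the recorded year, or the first of the recorded month) and the consent date, rounded down to a whole day.

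Make two accompanying corrections:

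- State whether the medication date rules also cover previous medications. If they do, never impute a start later than the known stop date. Do not assume that a drug of unknown start began before the 3-month pre-screening window.
- In the last bullet of the adverse event end-date list, replace *onset date* with *end date*, so that the onset rule alone governs a completely missing onset.

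The cost is a few lines of SAP wording and minor programming. No new data are needed and trial conduct does not change.

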#### 7.1.3 Adverse event collection

Adverse events and serious adverse events will be collected from the time of signing informed consent form and then at each visit until the end of the study.

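### SAP 5.2 sets certain incomplete AE onset dates to first dose without checking the end date, so an event that ended before dosing can be counted as treatment-emergent

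*SAP*

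**What the plan says.** SAP 5.2 has five rules for an incomplete AE onset date. Three of them lead to the first dose date:

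- Nothing known: "the AE start date will be imputed as the first date of study drug".
- Month and year known and equal to those of first dose: the rule reads "the year and the month are the corresponding year and month of the first dosing date, then the AE start date will be imputed", and the value assigned is again the day of first dose.
- Year only: the condition is "If only the year is available and the available year is the corresponding year of the first dosing date". The result is the same.

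The other two keep the recorded period. If the month and year differ from those of first dose, "then the AE start date will be imputed as the 1st date of the month". If only the year is known and it differs, "then the AE start date will be imputed as the January 1st of the year".

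None of the five refers to the end date of the event. The end-date rules that follow complete partial end dates (last day of the month, or 31 December) and are not linked back to onset.

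Pre-dose events do enter the database. Protocol 7.1.3 states: "Adverse events and serious adverse events will be collected from the time of signing informed consent form". Protocol 8.1.1 allows the first screening visit up to 42 days before randomization, and Protocol 8.2 schedules AE recording at S1, S2 and V1. SAP 5.12.1 and 5.12.2 divide events into pre-treatment AEs and TEAEs by timing relative to first dose, report the former separately, and make TEAEs the main focus of AE reporting. I found no override in either document for an event known to have ended before dosing.

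**The concern.** Imputing to first dose is a sensible conservative choice when the timing of an event is unknown. It is not sensible when a recorded end date already shows that the event was over before the first injection. The rule as written then produces a record that starts after it ends, and that record is likely to land in the TEAE tables, although the data show that it belongs with the pre-treatment events.

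Safety and tolerability are a primary endpoint (SAP 2.3), and the arms are small. One subject in 15 is close to the 7% incidence in which SAP 5.13 frames the sample size, so a single misplaced subject can be visible in a preferred-term row.

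**Working it through.** The documents give no figure on this point, so there is none to reproduce. The check is to apply the rules literally.

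**Inputs.** The onset and end-date rules are from SAP 5.2. The period and TEAE definitions are from SAP 5.12.1 and 5.12.2. The 42-day limit is from Protocol 8.1.1. The arm size of 15 is from SAP 5.13.

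**Step 1: a worked example.** The dates are invented for illustration. First dose is 20 March 2017 and the event has a recorded end date of 9 March 2017.

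| Recorded onset | Imputed onset | Start after end? | Class |
|---|---|---|---|
| missing | 20 Mar 2017 | yes, by 11 days | TEAE* |
| Mar 2017 | 20 Mar 2017 | yes, by 11 days | TEAE* |
| 2017 | 20 Mar 2017 | yes, by 11 days | TEAE* |
| Feb 2017 | 1 Feb 2017 | no | pre-treatment, correct |
| 2016 | 1 Jan 2016 | no | pre-treatment, correct |

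*If an onset on the dosing date counts as treatment-emergent. SAP 5.12.1 starts the post-treatment period after the first dose and does not say how the dosing date itself is classed. Treatment-emergent is the natural reading, since otherwise imputing unknown onsets to that date would keep them out of the TEAE tables. The impossible order of dates arises on either reading.

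**Step 2: how often each rule bites, given an incomplete date.** Assume that a pre-dose onset is uniform over the 42 days before dosing and that first doses are spread evenly over a 365-day year. That gives 365 × 42 = 15,330 combinations of dosing date and onset day.

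- Onset completely missing: all are moved to first dose, 100%.
- Only the year known: an onset stays put only if it falls in the previous calendar year. That occurs in 42 + 41 + … + 1 = 903 combinations, so 1 − 903/15,330 = 94% are moved.
- Only the day missing: with first dose on day d of a month, the d − 1 earlier days of that month are moved. Summed over the year this is 5,738 − 365 = 5,373, where 5,738 = 7 × 496 + 4 × 465 + 406 is the sum of the day-of-month numbers. So 5,373/15,330 = 35% are moved.

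These shares are conditional on an incomplete onset date. They do not estimate how many events in the trial will be affected.

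**Step 3: the weight of one subject.** The tables count subjects with any TEAE, or with at least one by system organ class and preferred term. A subject with no other TEAE at that level adds 1/15 = 6.7 percentage points to the arm, or 1/30 = 3.3 points if the two active arms are pooled. A subject who already has one adds 0. The event count, which SAP 5.12.2 also tabulates, rises by one either way.

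**Step 4: the effect of an end-date condition.** If first-dose imputation is withheld when the latest possible end date precedes first dose, the three misplaced rows in step 1 become pre-treatment and the other two do not change.

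**The case against.** The strongest reply is that the trigger is narrow. It needs an incomplete onset and an end date before dosing, within a window of at most 42 days with AEs recorded at S1, S2 and V1. Protocol 10.4 and 12.1 provide for queries and data cleanup, which could resolve such records before database lock. This stands as a reason to expect few cases. It does not remove the gap, because neither section names a check of AE start against end.

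A second reply is that an event known to have ended before dosing does not meet the TEAE definition in SAP 5.12.2, whatever its imputed date. That is fair as to intent. But the SAP does not say that the definition overrides the imputed date, and an imputed onset normally drives the flag.

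A reader might also infer more than the text supports:

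- **That every partial onset is moved to first dose.** Only three of the five rules do this. The other two already give the right class in the examples above.
- **That false events in the placebo arm would hide a true difference.** The rule is the same in every arm, and an event that resolved before dosing cannot be caused by treatment, so the expected addition is equal across arms. If a fraction q of subjects in each arm independently gains a false event, an arm's risk p becomes p + (1 − p)q, and a true risk difference is multiplied by (1 − q). At q = 1/15, an assumed value, the shrinkage is about 7% of the difference. The TEAE summaries are descriptive, with no between-arm test specified. Chance imbalance in arms of 15 is possible; systematic masking is not shown.
- **That each case costs 6.7 points.** That is the maximum. With seven injections and 78 weeks of follow-up, many subjects may already have a TEAE, and for them overall incidence does not move.

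**Conclusion.** The gap is real but minor. In three of five branches the onset rule ignores an end date that can settle the matter, and it can give an event a start after its own end. Counting such an event as a TEAE is the natural consequence, though not one the SAP spells out.

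The effect is 0 to 6.7 points of TEAE incidence per affected subject in an arm of 15, plus one in the event count for each record. The number of affected subjects is probably small and cannot be derived from the documents, which give no rate of incomplete onset dates. Nothing here shows bias between arms. This is an improvement worth making, not a threat to the trial's conclusions.

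**What to change.** Change only the three branches of SAP 5.2 that lead to the first dose date, along these lines:

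> Impute onset to the date of first dose only if the AE end date is missing, the event is ongoing, or the end date, taken at its latest possible value if partial, falls on or after first dose. Otherwise class the event as pre-treatment and impute onset as the later of the informed-consent date and the first day of any recorded onset month or year, but no later than the end date.

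The SAP's own rules already complete a partial end date to its latest possible value, so the test needs nothing new. In the example, with consent assumed on 10 February 2017, a missing onset or *2017* becomes 10 February and *Mar 2017* becomes 1 March, all before the end on 9 March. Imputing the consent date outright would be simpler, but it would put the *Mar 2017* event in February, against the record. Extending it to the other two branches could replace dates that already agree with the record. A record whose end date precedes consent lies outside the AE collection window and should be queried.

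Also add one sentence stating that an onset imputed to the dosing date counts as treatment-emergent.

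The cost is one clause and one sentence in the SAP. No new data are needed.
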